9.4 Reporting Procedures

9.4.1 *Unanticipated Problem Reporting to IRB and NIDCR*

Incidents or events that meet the OHRP criteria for unanticipated problems require the creation and completion of an unanticipated problem report form by the Co-PIs. The report will include the following information when reporting an adverse event, or any other incident, experience, or outcome as an unanticipated problem to the IRB:

- appropriate identifying information for the research protocol, such as the title, investigator's name, and the IRB project number;
- a detailed description of the adverse event, incident, experience, or outcome;
- an explanation of the basis for determining that the adverse event, incident, experience, or outcome represents an unanticipated problem;
- a description of any changes to the protocol or other corrective actions that have been taken or are proposed in response to the unanticipated problem.

To satisfy the requirement for prompt reporting, unanticipated problems will be reported using the following timeline:

- Unanticipated problems that are serious adverse events will be reported to the IRB and to NIDCR within 24 hours if death or a life-threatening event or within 72 hours for all other serious adverse events.
- Any other unanticipated problem will be reported to the IRB and to NIDCR within 7 days of the investigator becoming aware of the problem.
- All unanticipated problems should be reported to appropriate institutional officials (as required by an institution's written reporting procedures). The IRB will then report to the supporting agency head (or designee), and OHRP within one month of the IRB's receipt of the report of the problem from the investigator.

All unanticipated problems will be reported to NIDCR's centralized reporting system via Rho Product Safety:

- Product Safety Fax Line (US): [name]
- Product Safety Fax Line (International): [contact]
- Product Safety Email: [contact]

General questions about SAE reporting can be directed to the Rho Product Safety Help Line (available 8:00AM – 5:00PM Eastern Time):

- US: [name]
- International: [contact]

9.4.2 Serious Adverse Event Reporting to NIDCR

For any AE meeting the specified Serious Adverse Event criteria, the CO-PIs or their designee will submit an SAE form to NIDCR's centralized safety system via Rho Product Safety. This report may be sent by fax or email. Once submitted, Rho Product Safety will send a confirmation email to the investigator within 1 business day. The investigator should contact Rho Product Safety if this confirmation is not received. This process applies to both initial and follow-up SAE reports.

SAE Reporting Contact Information:

- Product Safety Fax Line (US): [name]
- Product Safety Fax Line (International): [contact]
- Product Safety Email: [contact]

General questions about SAE reporting can be directed to the Rho Product Safety Help Line (available 8:00AM – 5:00PM Eastern Time):

- US: [name]
- International: [contact]

The study clinician will complete a Serious Adverse Event Form and submit via fax or email within the following timelines:

- All deaths and immediately life-threatening events, whether related or unrelated, will be recorded on the Serious Adverse Event Form and submitted to Product Safety within 24 hours of site awareness.
- Serious adverse events other than death and immediately life-threatening events, regardless of relationship, will be reported by fax within 72 hours of site awareness.

All SAEs will be followed until resolution or stabilization.

10 STUDY OVERSIGHT

Study oversight will be under the direction of the study PIs, [name] (lead administrative and fiscal PI), [name], and the NIDCR. The study PIs will have weekly scheduled meetings to review study progress and monthly meetings with NIDCR and the DCC.

In addition to the PI's responsibility for oversight, study oversight will be under the direction of a Data and Safety Monitoring Board (DSMB) composed of members with appropriate clinical, statistical, scientific, and ethical expertise. The NIDCR will appoint the Board. The DSMB will meet annually to assess safety and efficacy data, study progress, and data integrity for the study. If concerns arise, more frequent meetings may be held. The DSMB will operate under the rules of an NIDCR-approved charter that will be approved at the organizational meeting of the DSMB. The DSMB will provide recommendations to the NIDCR.

11 CLINICAL SITE MONITORING

Clinical site monitoring is conducted to ensure that the rights of human subjects are protected, that the study is implemented in accordance with the protocol and/or other operating procedures, and that the quality and integrity of study data and data collection methods are maintained. Monitoring for this study will be performed by NIDCR's Clinical Research Operations and Management Support (CROMS) contractor. The monitor will evaluate study processes and documentation based on NIDCR standards and the International Conference on Harmonisation (ICH), E6: Good Clinical Practice guidelines (GCP).

Details of clinical site monitoring will be documented in a Clinical Monitoring Plan (CMP) developed by the CROMS contractor, in collaboration with the NIDCR Office of Clinical Trials and Operations Management (OCTOM) and the NIDCR Program Official. The CMP will specify the frequency of monitoring, monitoring procedures, the level of clinical site monitoring activities (e.g., the percentage of subject data to be reviewed), and the distribution of monitoring reports. Some monitoring activities may be performed remotely, while others may take place at the study site(s). Staff from the CROMS contractor will conduct monitoring activities and provide reports of the findings and associated action items in accordance with the details described in the CMP. Documentation of monitoring activities and findings will be provided to the site study team, the study PIs, OCTOM, and the NIDCR. The NIDCR reserves the right to conduct independent audits as necessary.

12 STATISTICAL CONSIDERATIONS

12.1 Study Hypotheses

Primary hypothesis 1: Those receiving OHT will have lower 24 month incidence of any new caries, compared to those receiving CWT.

Primary hypothesis 2: The OHT effect on new caries at 24 months will be mediated through Social Cognitive Theory constructs (self-efficacy, motivation, and outcome expectations). We will examine indirect effects of OHT through self-efficacy, motivation, and outcome expectations at 2 months, to potentially increased motivation and oral health behavior at 4 months (end of intervention) to new caries at 12 and 24 months. We will also examine indirect effects of OHT through self-efficacy, motivation, and outcome expectations at 4 months (end of treatment), to potentially increased motivation and oral health behavior at 12 months and to new caries at 12 and 24 months.

Secondary hypothesis 1: We hypothesize that the total cost of OHT implementation will be more cost-effective than standard of care (e.g., oral health anticipatory guidance).

Secondary hypothesis 2: Those receiving OHT will have better pediatric oral health behaviors (tooth brushing, diet, sugar-sweetened beverages, fluoride toothpaste use, preventive dental visits, and oral assessment by parents) at 4 months (end of intervention), 12 months, and 24 months, compared to those receiving CWT.

Secondary hypothesis 3: Those receiving OHT will have better oral health behaviors (tooth brushing, dental visits), oral health knowledge, and attitudes at 4 months (end of intervention), 12 months, and 24 months, compared to those receiving CWT.

Exploratory Analyses: These analyses will explore whether the effect of OHT vs. CWT on new caries at 24 months is greater in subpopulations defined by race/ethnicity, insurance coverage, parent education level, child's prior caries experience, parent depressed mood, and intervention dose/engagement.

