3 OBJECTIVES

3.1 Study Objectives

Primary Aims:

1. To test the efficacy of the OHT intervention in a theory-based, fully powered, dose-matched design with objective clinical measurement of caries. Parents of children <7 years old attending one of our partner pediatric clinics will be randomized to receive either OHT or CWT. H₁: Those receiving OHT will have lower 24- month incidence of caries vs. those receiving CWT, as assessed by clinical exam. Clinical exams will take place at baseline and 12-and 24- months later.
2. To assess the mechanisms through which intervention effects occur (mediators). H₂: OHT will differentially change Social Cognitive Theory constructs (motivation, self-efficacy, outcome expectations) over time vs. CWT. We will test the mediational effect on caries. Mechanisms will be assessed through text messaging assessments during the intervention, and through self-report surveys at baseline, and 2, 4, 12 and 24- months after baseline.

Secondary Aims:

1. To perform budget impact analyses of pediatric clinic adoption of the OHT intervention to determine the financial consequences of adoption, diffusion, and sustainability. The budget impact analyses will include interviews with key stakeholders.
2. Examine change in pediatric oral health behaviors (e.g. tooth brushing, diet, sugar sweetened beverages, fluoride toothpaste use, preventive dental visits, and 'lift the lip' oral assessment by parents). These variables will be assessed at baseline, 4, 12, and 24 months after baseline.
3. To assess the effect of the intervention on the parent's oral health status, knowledge, attitudes, and behaviors (spill-over effect). These variables will be assessed at baseline, 4, 12, and 24 months after baseline.
4. To identify subpopulations for whom the intervention has the greatest effect (moderators; e.g., race/ethnicity, insurance coverage, parent educational level, parent depressed mood, child's prior caries experience and intervention dose/engagement). All moderators will be assessed at baseline, except for intervention dose/engagement, which will be assessed during the course of text message delivery.

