Number of goals set and completed will be assessed during the TM program. OHT will set goals to brush (or supervise brushing) their children's teeth and CWT will set goals to read to their children. Goals set and completed are automatically tracked in the AH TM platform system. We will also assess whether or not participants 'opt in' to participating in 'challenge weeks.' For OHT, this will entail setting a goal of brushing every day, twice per day. For CWT, this will entail reading to their child every day. Both groups will be assessed each day for their adherence.

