Parent depressed mood: We will use the short-form of the Center for Epidemiologic Studies Depression Scale (CESD-R- 10; Kohut et al., 1993). The correlation between the long and short-forms is $r=.91$. Cronbach's alpha = .86. This measure will be assessed at baseline, 4, 12, and 24 months after baseline.

History of dental care (parent and child). This measure will be assessed at baseline, 12 and 24- months. We will use items from the BRFQ (Albino et al., 2017).

Perception of dental visits: We will assess parental attitude toward taking their child to the dentist. This measure will be assessed at all measurement points. We will use items from the BRFQ (Albino et al., 2017).

Fluoride varnish. This measure will be assessed at baseline, 12 and 24- months. We will use items from the BRFQ (Albino et al., 2017).

Child oral health quality of life. We will use the Child Oral Health Impact Profile-Reduced scale (SF-19), which shows good reliability and validity to measure oral health related quality of life (Broder et al., 2012). This measure will be assessed at baseline, 4, 12, and 24 months after baseline.

Intervention Dose and Engagement: number of texts sent; percent of texts responded to, number of unprompted responses, use of program features, topics chosen, and goals set/completed.

Program Satisfaction. We adapted the Mobile App Rating Scale (MARS; Stoyanov et al., 2015) to measure satisfaction with the text messaging program (e.g., would you recommend this program; '1'= not at all to '5' definitely). Our other measures of program satisfaction that we adapted from the MARS are: showing the TMs to others (yes/no); perceived helpfulness of TMs to family/friends; how much longer they want to receive the program; and satisfaction with each of the proposed program components (e.g., setting goals, choosing topics) and structure (e.g., time of day TMs received, frequency). The MARS also measures perceived impact of the intervention, and we adapted it for oral health. We measure the perceived impact of the program on their own attitudes towards their child's oral health and oral health practices.

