6.2 Administration of Intervention

The TM intervention is automated and interactive. The program will begin sending TMs within 24- hours of randomization. Both OHT and CWT will be 4-months in duration, with a 1-month booster session that will occur 12 months after baseline (8 months after the end of the 4 month program). TMs will be delivered approximately twice each day in Month 1, and once per day in Months 2-4 (exclusive of brief assessment questions which occur several times per week).

During the booster session (at 12 months after baseline), TMs will be delivered approximately twice per day, exclusive of brief assessment questions. Brief assessment questions will occur several times per week. The number of texts, dose, and duration will be equivalent between the two groups. Participants in both groups will choose 'choice topics' each week, and will be assessed weekly via TM on core topics (brushing for OHT; reading for CWT) and mediators (motivation, self-efficacy and outcome expectations). Monthly assessments include dental visits (OHT) or safety (CWT)

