among controls will be reduced an additional 25% (Weinstein et al, 2004) or from 31.7% to **23.8%**. Kressin et al. (2009) found a 44.2% reduction in caries incidence due to the brief patient centered counseling intervention during the pediatric well child visit. If we assume a similar effect from the daily text messaging intervention, we would expect a **13.3%** incidence of caries in the intervention group compared to 23.8% incidence in the control group (accounting for possible FV effect). To be slightly more conservative, we can use the 40% reduction in caries incidence found by Weinstein et al in his intervention and in the Marinho et al., 2013 Cochrane review. This would result in **14.3%** caries incidence for the intervention group. In this scenario, we would need 300 parent-child dyads at our 24 month follow-up to have an estimated 84% power (2 tailed) to detect a 9.5% difference in caries incidence between groups with alpha=0.05 and according to the standard chi-square test.

Our second primary hypothesis will examine the mechanism of the OHT effect, examining mediation through Social Cognitive Theory constructs of self-efficacy, motivation, and outcome expectations. Statistical power for tests of indirect effects of OHT through a mediator will be calculated using the joint effects approach; there is 80% power of detecting an indirect effect if the power of showing an association between OHT and the mediator, and an association between the mediator and 24 month caries incidence, are both 90%. We have 80% power of showing an indirect effect of a continuous mediator if intervention (OHT vs. CWT) explains 2% of the mediator ($R^2=.02$), and if a 1 standard deviation increase in the mediator leads to a 30% reduction in the odds of caries (an OR=0.70). This study was powered to detect an OHT effect in the overall sample. Secondary analyses examining whether the OHT effect varies across subpopulations defined by race/ethnicity, insurance coverage, maternal education level, or child's prior caries experience will have lower power. These analyses should therefore be considered exploratory.

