
Aims 2 and 3. We will compare changes in these behaviors over time in OHT vs. CWT using mixed effects logistic regression models (for dichotomous outcomes) and mixed effects linear regression models (for continuous outcomes). Changes in these behaviors from baseline to 2, 4, 12, and 24 months will be described through odds ratios and 95% confidence intervals for logistic models, and slopes for linear models. Differences in changes over time for OHT vs. CWT will be tested through group by time interaction terms.

Aim 4: To identify subpopulations for whom the intervention has the greatest effect, we will analyze moderators; e.g., race/ethnicity, insurance coverage, parent educational level, and child's prior caries experience. This aim focuses on moderator effects (also known as effect modification) for incident caries over 24 months. We will use logistic regression models with multiplicative interaction terms (treatment group x moderator) to compare the efficacy of OHT across subpopulations.

17. Missing data: We will gather follow-up information and reasons for dropout regardless of treatment completion, censoring at the point of loss. We will examine the extent of drop-out, and identify characteristics associated with drop-out through logistic regression. Given drop-out does not exceed the expected rate of 30%, primary analyses will be based on available data. Secondary analyses will account for missing data and explore the potential impact of drop-out on study findings. We will describe the robustness of our findings with respect to missing data using inverse probability weighting. This approach to handling missing data has two steps: 1) develop propensity scores for missing data, which involves using logistic regression to model the probability of being followed to the 24 month visit as a function of baseline variables, including history of caries; and 2) using the inverse of the propensity scores (predicted probabilities from the first step) to serve as weights in our logistic regression model of new

primary teeth caries. Provided the data are missing at random (MAR), that is, the probability of missingness can be fully explained by observable data, this approach produces asymptotically unbiased estimates. If there is sufficient missing data, and a concern that data may be missing not at random, we will also consider pattern mixture models to perform a sensitivity analysis of the potential impact of missingness.

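### Intervention dose/engagement is measured after randomisation but listed as a moderator, so a treatment-by-engagement interaction can be biased if engagement relates to caries risk differently in the two arms

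*Combined protocol and SAP*

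**What the plan says.** The Protocol Summary (secondary objective 4), section 3.1 (secondary Aim 4) and the exploratory paragraph of section 12.1 all list dose/engagement as a moderator. In section 12.1 the list of variables defining subpopulations for the effect on new caries ends with "parent depressed mood, and intervention dose/engagement".

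Section 3.1 says that all moderators are taken at baseline, "except for intervention dose/engagement, which will be assessed during the course of text message delivery". Section 6.2 fixes the order of events: "The program will begin sending TMs within 24- hours of randomization". All engagement data are therefore post-randomisation.

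Section 3.2.2 gives the components: "number of texts sent; percent of texts responded to, number of unprompted responses, use of program features, topics chosen, and goals set/completed". Section 3.2 shows that at least one of them means different things by arm: "OHT will set goals to brush (or supervise brushing) their children's teeth and CWT will set goals to read to their children".

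For Aim 4, section 12.4 gives one method: "We will use logistic regression models with multiplicative interaction terms (treatment group x moderator) to compare the efficacy of OHT across subpopulations". Its list of moderators is introduced as examples and does not name engagement, but no other method for engagement appears anywhere. On the status of subgroup analyses, section 12.2 says "These analyses should therefore be considered exploratory". The reason given there is low power, and its list of subgroups does not include engagement.

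**The concern.** A treatment-by-moderator term reads as effect modification because a baseline variable has the same meaning and the same relation to prognosis in both randomised arms. A post-randomisation response carries no such guarantee. Parents with high engagement in OHT are those who responded to brushing and dental-visit content; those with high engagement in CWT responded to reading and safety content. If the two selections relate differently to the child's underlying caries risk, the arms are not comparable within an engagement level, and the interaction reflects that difference as well as any real modification.

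The plan also uses one component in two roles. Goals set and completed appear under the mediators in section 3.2.1 and again inside dose/engagement, among the moderators in section 3.2.2. A variable placed on the path from OHT to caries is not a subgroup fixed before treatment.

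At stake is the meaning of an exploratory finding such as an OHT benefit confined to engaged parents, which could appear when no child benefits or when every child benefits equally.

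**Working it through.** **Plan's own figure.** The documents state no figure for the moderator analyses. The nearest is the primary comparison in section 12.2: 23.8% versus 14.3%, 300 per arm, two-sided 0.05, stated power 84%.

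- Pooled proportion: (0.238 + 0.143)/2 = 0.1905. Null SE: √(2 × 0.1905 × 0.8095/300) = 0.03206.
- Alternative SE: √((0.238 × 0.762 + 0.143 × 0.857)/300) = 0.03183.
- Power: Φ((0.095 − 1.96 × 0.03206)/0.03183) = Φ(1.01) = 0.844. This reproduces, and nothing below changes it.

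**Illustration of the bias.** From the documents: 300 per arm and an incidence near the planned 23.8% (about 23% in the simulation). Assumed: a favourable parental trait U (standard normal) with a caries log odds ratio of −0.5 per SD; standardised engagement E with correlation r_OHT or r_CWT with U; no OHT effect for any child. The fitted model is logistic in T, E and T × E.

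The mean of U given E is rE, so the slope of the log odds on E is roughly −0.5r within each arm. The spurious interaction is therefore roughly −0.5 × (r_OHT − r_CWT), and the apparent OHT odds ratio at ±1 SD of engagement is roughly the exponential of ± that value. The last column is simulated, with 4,000 trials per row.

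| r_OHT | r_CWT | Approx. interaction | Approx. OR at +1 SD / −1 SD | False interaction rate |
|---|---|---|---|---|
| 0.5 | 0.5 | 0 | 1.00 / 1.00 | 4.4% |
| 0.5 | 0.4 | −0.05 | 0.95 / 1.05 | 5.1% |
| 0.5 | 0.3 | −0.10 | 0.90 / 1.11 | 7.6% |
| 0.6 | 0.3 | −0.15 | 0.86 / 1.16 | 11.9% |
| 0.7 | 0.2 | −0.25 | 0.78 / 1.28 | 22.9% |

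In the last row the simulated odds ratios are about 0.76 and 1.24, close to the approximation.

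**Direction.** With the correlations reversed (0.3 in OHT, 0.6 in CWT) the test rejects in about 11% of trials, but in only 0.3% does it point to OHT working in engaged parents. That particular artefact is systematic only when the link is stronger in OHT.

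**A real, uniform effect does not protect.** A second model used binary engagement (half high in each arm), and engagement depended on latent risk in OHT (log odds ratio −1 per SD of risk) but not in CWT. Three strengths of the risk-caries link were tried: log odds ratio 0.5, 1.0 and 1.5 per SD. False interaction rates were 18%, 46% and 68% with no effect. With the planned effect, 14.3% versus 23.8% and the same for every child, they were 15%, 39% and 61%. With the same link in both arms they stayed near 5% in both settings. This is a deliberately strong contrast between arms.

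**The case against.** The strongest reply has four parts.

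- **Matching.** The arms are matched on dose, duration, frequency, features and engagement strategies, and the number of texts is designed to be equivalent. Much of what drives response may therefore be common to both arms, and with equal links there is no inflation. This stands: it makes the bias less likely and rules out treating it as established. It does not exclude the bias, because goals and topics differ by arm.
- **Exploratory status.** Section 12.1 labels these analyses exploratory, and the primary analysis keeps followed participants regardless of engagement. This limits the consequences. But the reason given in section 12.2 is low power, which is a matter of precision; a larger sample would not remove this bias.
- **Section 12.4 does not name engagement.** Applying the interaction model to it is an inference, and no engagement score or cut-point is defined. That is fair. But two sections and the summary call engagement a moderator, and section 12.4 offers one method for moderators.
- **Size.** The larger rates need a wide gap between arms. With 0.5 versus 0.4 the rate is about 5%. This also stands.

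A reader might infer that engaged OHT and engaged CWT parents are in fact different kinds of parent, or that a claim about engaged parents is the one most likely to be disseminated. The documents support neither. They show that engagement content differs by arm, and the dissemination work they describe is the budget impact analysis and stakeholder interviews.

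**Conclusion.** The concern holds as a risk of bias in one exploratory analysis. The plan names a post-randomisation variable as a moderator and gives no method for it other than a treatment-by-moderator interaction. That interaction can mislead if the engagement-risk relation differs between arms. Under the assumed correlations the false interaction rate runs from about 5% (equal or nearly equal links) through 8% and 12% to 23% (0.7 versus 0.2). The documents give no information on where in that range the trial lies, and the direction of any artefact depends on which arm has the stronger link.

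It would be wrong to infer that the interaction will be false, or that the efficacy conclusion is at risk. The primary test, the 84% power and the enrolment of 850 do not depend on it.

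**What to change.** Delete dose/engagement from the moderator lists in the Protocol Summary (secondary objective 4), section 3.1 (Aim 4) and section 12.1. State in section 12.4 that treatment-by-moderator models use baseline variables only, and align its list with the other sections; it currently omits parent depressed mood as well. Report engagement descriptively and within arm, as a process measure without causal interpretation.

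Optionally, if the effect among engagers is of interest, add an exploratory complier-average analysis with randomisation as the instrument and a pre-stated OHT engagement threshold. It must state its exclusion restriction: no OHT effect below the threshold. That is doubtful here, because a parent who does not respond may still read the texts. For example, suppose half the parents pass the threshold and gain d, and the rest gain d/2. The overall effect is 0.5d + 0.25d = 0.75d, and the complier estimate is 0.75d/0.5 = 1.5d, an overstatement of 50%. The interval is also wider than for the overall effect.

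The cost is protocol and analysis-plan wording and the loss of one exploratory subgroup analysis. No new data are needed.
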